7.5. Association Analysis of Biomarkers with Clinical Efficacy Endpoints

The primary endpoint is ORR, defined as the proportion of subjects who achieve partial response or better [PR(+L) or better], as assessed by the investigators at or prior to initiation of subsequent anti-cancer therapy. The primary efficacy analysis of ORR will be conducted at performed 6 months after the last subject has received the first dose of study medication, or earlier if that subject discontinues study therapy. The analysis will be based on the response-evaluable or biomarker populations, as see appropriate.

In addition, the following secondary endpoints will be evaluated if there are sufficient events to warrant the analysis:

- Duration of Response.
- Time to Response.
- Progression-free Survival and Overall Survival.
- Best overall Response.

7.5.1. Level of Significance

All tests will be 1-sided. The primary efficacy endpoint will be tested at the overall significance level of 0.025. Nominal p-values will be presented for all statistical analyses, if applicable.

7.5.2. Missing Data Handling

If >90% of subjects have missing value for a particular biomarker, or if all subjects have the same value for a biomarker, then only the frequencies will be summarized and that biomarker will be removed from further analysis.

If a subject has missing data for a clinically defined endpoint, that subject will be excluded from that particular association analysis but included in other analyses where data is available.

7.5.3. Data Transformation and imputation

No transformation will be performed on any of the clinical data other than what was transformed as part of the clinical statistical analysis. If deemed applicable, biomarker data may be log (base 2 or 10) transformed if the data distribution is not normal or otherwise skewed. Shapiro-Wilk's test will be used to determine normality for baseline only.

7.5.4. Outlier Detection and Handling

No outlier handling will be performed

7.5.5. Biomarker Data Analysis Methods for PDL1, and NGS and GEP (if available)

- Median, mean (SD), and range for continuous variable or N and frequency (%) for categorical variables will be reported for all-treated versus the biomarker populations for selected demographic and baseline characteristic variables including the biomarker stratification cohorts.
- The number of subjects (N) and the associated percentage (%) will be presented to facilitate the evaluation of the response rate. The median duration of response (arising from Kaplan-Meier estimate) between 1) PDL1 IHC option 1/2 subgroups (i.e., not elevated/negative vs. elevated/positive); 2) NGS subgroups (i.e., negative vs. positive); 3) GEP subgroups (i.e., >median vs. <=median) will also be reported.

The relationship between 1) PDL1 not elevated (or negative) vs. elevated (or positive) subgroups; 2) NGS negative vs. positive subgroups; 3) GEP subgroups >median vs. <=median subgroup for duration of response, progression-free survival and overall survival will be evaluated by the Kaplan-Meier method. If the number of subjects is ≤ 7 then Kaplan-Meier analyses are unnecessary.

- For each of the biomarker stratification cohort, Fisher exact test will be used to test the association on the response between 1) PDL1 subgroups (not elevated and elevated for option 1; negative and positive for option 2); 2) NGS subgroups (negative vs. positive); 3) GEP subgroups (>median vs. <=median)
- Descriptive summary statistics [i.e., mean (SD), median and range] will be used to evaluate time to initial response and best response of the PDL1, NGS and GEP subgroups for each of the biomarker stratification cohort.

7.5.6. Biomarker Data Analysis Methods for Flow Cytometry T-cell Type Panel Data

- Data arising from T-cell type panel collected over time will be descriptively summarized for each biomarker stratification cohorts. The corresponding mean (\pm se) over time line plot for each biomarker stratification cohorts will be generated. In Addition, mean change and percent change from baseline will also be descriptively summarized. The corresponding mean change and percent change from baseline values will be plotted.

- Mean values for each T- cell type over times by response group (i.e., non-responder and responder) will be reported for the biomarker stratification groups – CLL, FL, DLBCL, ABC-DLBCL, GCB-DLBCL and Richter's. For each cell type, the corresponding mean (\pm se) line and box plots over time by response group for each selected biomarker stratification group will be generated. Similarly, the mean (\pm se) line plot over time by progression group (i.e., progressor and non-progressor) for each cell type for selected biomarker stratification group will also be generated.
- Paired t-test will be performed to compare the mean at baseline vs the mean at each post baseline time point for each cell type and for each selected biomarker stratification group by respond group and progression group, respectively.

REFERENCES

APPENDICES

1. Appendix A

Preferred terms for CNS hemorrhage are as follows:

- Acute haemorrhagic leukoencephalitis
- Basal ganglia haemorrhage
- Brain stem haemorrhage
- Brain stem haematoma
- Central nervous system haemorrhage
- Cerebellar haematoma
- Cerebellar haemorrhage
- Cerebral arteriovenous malformation haemorrhagic
- Cerebral haematoma
- Cerebral haemorrhage
- Cerebral microhaemorrhage
- Encephalitis haemorrhagic
- Epidural haemorrhage
- Extradural haematoma
- Haemorrhage intracranial
- Haemorrhagic cerebral infarction
- Haemorrhagic stroke
- Haemorrhagic transformation stroke

- Intracerebral haematoma evacuation
- Intracranial haematoma
- Intracranial tumour haemorrhage
- Intraventricular haemorrhage
- Pituitary haemorrhage
- Putamen haemorrhage
- Ruptured cerebral aneurysm
- Spinal cord haemorrhage
- Spinal epidural haematoma
- Spinal epidural haemorrhage
- Spinal subarachnoid haemorrhage
- Spinal haematoma
- Spinal subdural haematoma
- Spinal subdural haemorrhage
- Subarachnoid haemorrhage
- Subdural haematoma
- Subdural haemorrhage
- Subgaleal haematoma
- Thalamus haemorrhage

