2. OBJECTIVES AND HYPOTHESIS

2.1. Objectives

Primary Objective

Part A (Dose Optimization Cohorts): The primary objective of Part A is to determine whether ibrutinib and nivolumab can be safely combined and to establish the recommended Phase 2 dose (RP2D) for this combination in subjects with hematological disorders.

Part B (Expansion Cohorts): The primary objective of Part B is to determine the preliminary activity of the ibrutinib/nivolumab combination regimen in subjects with relapsed/refractory CLL/SLL and poor prognosis (deletion 17p or deletion 11q), relapsed/refractory FL, relapsed/refractory DLBCL, or Richter syndrome in comparison to historical results.

Secondary Objectives

The secondary objectives are:

- To evaluate the safety profile of the ibrutinib and nivolumab combination regimen
- To assess overall response rate (ORR), duration of response, duration of stable disease, progression-free survival rate at 1 year, and overall survival at 1 year of the ibrutinib and nivolumab combination regimen
- To characterize and explore the pharmacokinetic profile of ibrutinib and nivolumab compared with existing single-agent treatment data; and the potential relationships between ibrutinib and nivolumab metrics of exposure with relevant clinical or biomarker information (Part A and B)

Exploratory Objectives

- To characterize the molecular effects of the ibrutinib and nivolumab combination regimen on tumor cells and the immune response; and identify biomarkers of response or resistance to the combination
- To evaluate the immunogenicity of nivolumab

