12.6. Biomarker Analyses

Analyses are planned to identify biomarkers that are indicative of the mechanisms of action of the drug or predictive of efficacy for the combination. The associations of biomarkers with clinical response or time-to-event endpoints will be assessed using the appropriate statistical methods (analysis of variance [ANOVA], categorical, or survival model), depending on the endpoint. Correlation of baseline expression levels or changes in expression levels with response or time-to-event endpoints will identify responsive (or resistant) subgroups.

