7.3. Biomarker Stratification Groups

Biomarker analysis will be performed with no patient stratification (all patients) and with stratification by dose expansion cohort by indication (i.e., biomarker stratification cohort) as shown:

- A. CLL
- B. CLL only del 17p
- C. CLL only del 11q
- D. FL
- E. DLBCL
- F. ABC-DLBCL (if available)
- G. GCB-DLBCL (if available)
- H. Richter Syndrome
- I. ABC-like Richter's (if available)
- J. GCB-like Richter's (if available)

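### For the T-cell panel, the SAP tests change within response and progression groups but never between them, and its one-sided biomarker tests have no stated direction

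*SAP*

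**What the plan says.** Protocol 2.1 lists among its exploratory objectives to "identify biomarkers of response or resistance to the combination". Protocol 12.6 turns this into an analysis: "The associations of biomarkers with clinical response or time-to-event endpoints will be assessed" by ANOVA, categorical or survival models, and it covers changes in expression as well as baseline levels.

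SAP 7.4 defines the T-cell panel as 13 reported and 10 calculated measures, taken at C1D1, C1D7, C3D1 and end of treatment or progression. For this panel SAP 7.5.6 gives two kinds of output by outcome group:

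- Descriptive: "Mean values for each T- cell type over times by response group (i.e., non-responder and responder) will be reported" for the named diseases, with line and box plots, and similar line plots by progression group.
- Inferential: "Paired t-test will be performed to compare the mean at baseline vs the mean at each post baseline time point". This test is repeated for every T-cell measure, separately inside each response group and inside each progression group of the selected disease cohorts.

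SAP 7.5.1 sets the testing rule for the whole biomarker section: "All tests will be 1-sided. The primary efficacy endpoint will be tested at the overall significance level of 0.025". It calls the p-values nominal. Neither 7.5.1 nor 7.5.5 nor 7.5.6 states a direction for any marker.

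For PD-L1, NGS and GEP, SAP 7.5.5 does specify a between-group test: Fisher's exact test of marker subgroup against response in each stratification cohort. It adds Kaplan-Meier estimates by marker subgroup for duration of response, PFS and OS.

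**The concern.** A marker is linked to response if its change differs between responders and non-responders. A paired test inside one group asks something else: did that group's mean move? Two such tests side by side do not make a comparison, because each p-value depends on the size of its group as well as on the change. A cell type that treatment shifts equally in everyone can be significant in the larger group and not in the smaller, and so be read as a marker of response or resistance. The error also runs the other way: when both groups move, both tests can be significant and a real difference in the size of the change is hidden.

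Sidedness is a separate gap. The objective names response and resistance, which are opposite directions of association. "All tests will be 1-sided" with no direction means either that one direction goes untested or that the direction is chosen once the data are seen. In the second case the level actually used is 0.05 two-sided, not the stated one-sided 0.025.

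**Working it through.** **The plan's own figure.** The biomarker section gives no sample size or power. The only planning figure is 32 response-evaluable subjects per Part B cohort (SAP 1.4: ORR 20% versus 38%, one-sided 0.1, power at least 0.8). It reproduces by exact binomial: rejecting at 10 or more responses out of 32 has error 0.090 and power 0.833. It concerns ORR and is used here only for a plausible cohort size.

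**Inputs.** From the documents: 32 per cohort, an alternative ORR of 38%, and the one-sided 0.025 of SAP 7.5.1. The SAP words that level for the primary efficacy endpoint; applying it to the paired tests is an assumption. Also assumed: all 32 have paired samples, the split is 12 and 20 (38% of 32 is about 12), and the standardised change d (mean change divided by the SD of change) is the same in both groups, so the marker has no link to response.

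**Step 1: power of each within-group paired t-test.** Power = P(T > t with n−1 degrees of freedom at 0.975), where T is noncentral t with noncentrality d√n. The critical values are 2.201 for n = 12 and 2.093 for n = 20. At d = 0.5 the noncentralities are 0.5√12 = 1.73 and 0.5√20 = 2.24.

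**Step 2: chance that exactly one group is significant.** With independent groups and powers a and b, this is a(1−b) + b(1−a). At d = 0.5: 0.353 × 0.436 + 0.564 × 0.647 = 0.519.

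| d (same in both groups) | Power, n = 12 | Power, n = 20 | Exactly one significant |
|---|---|---|---|
| 0 | 0.025 | 0.025 | 0.049 |
| 0.3 | 0.156 | 0.246 | 0.326 |
| 0.5 | 0.353 | 0.564 | 0.519 |
| 0.8 | 0.714 | 0.924 | 0.319 |
| 1.0 | 0.883 | 0.989 | 0.126 |

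The last column is the same if responders are the 20 and non-responders the 12. With a 6/26 split (near the 20% null ORR) it is 0.35, 0.62 and 0.64 at d = 0.3, 0.5 and 0.8.

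**Step 3: the reverse error.** With true changes of 1.4 SD (n = 12) and 0.6 SD (n = 20), the powers are 0.993 and 0.721. Both tests are significant with probability 0.993 × 0.721 = 0.72, although the changes differ by 0.8 SD.

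**Step 4: the direct comparison.** A two-sample t-test on change has noncentrality δ/√(1/12 + 1/20), where δ is the between-group difference in SD units. Its false-positive rate is 0.025 one-sided (0.05 two-sided) whatever the common change. Power at one-sided 0.025 is 0.26, 0.56 and 0.75 for δ = 0.5, 0.8 and 1.0.

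**Step 5: sidedness.** A paired test with n = 20 pointed the wrong way has power of at most 0.0006 for d of 0.3 or more. For Fisher's test with 16 versus 16 subjects and response rates of 60% and 16% (assumed), power at one-sided 0.025 is 0.62 in the chosen direction and about 0 in the other. A two-sided 0.05 test has 0.62 either way. Two-sided 0.05 uses the same t critical value as one-sided 0.025, so nothing is given up in the favoured direction.

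**The case against.** Much can be said for the plan. The T-cell means are shown side by side by response and progression group, so a reader can see whether the groups diverge, and the SAP nowhere says that significance in one group makes a marker predictive. The analyses are exploratory with nominal p-values, and Protocol 10.5 allows biomarker work to be deferred or not performed. All this limits the consequences. It does not supply the missing comparison: Protocol 12.6 plans to relate changes to outcome, and the only p-values that 7.5.6 produces do not do that.

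Three stronger readings are tempting, and the documents do not support them.

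- A reader might infer that the SAP cannot identify any marker of response or resistance. SAP 7.5.5 tests PD-L1, NGS and GEP directly against response. The missing comparison concerns the T-cell panel only; the other markers are touched only by the sidedness point.
- A reader might infer that response associations will be distorted by pooling diseases, because SAP 7.3 says "Biomarker analysis will be performed with no patient stratification (all patients") as well as by indication. No association test is clearly attached to that unstratified analysis. The Fisher tests are per stratification cohort, the T-cell results by response group are for named diseases, and the GEP median is taken within disease group.
- A reader might infer that picking the direction afterwards produces an unacceptable error rate. It gives 0.05 two-sided, the conventional level and the one recommended here. In the Fisher example with equal response rates of 38%, the exact error rises only from 0.009 to 0.019. The fault is an unclear rule and a mislabelled level.

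**Conclusion.** The point holds for the T-cell panel: the SAP has no test of whether change differs between responders and non-responders, or between progressors and non-progressors, and so falls short of Protocol 12.6. Under the stated assumptions, a marker that moves equally in both groups is significant in exactly one of them 13% to 52% of the time for d between 0.3 and 1.0 at a 12/20 split. With no change at all the figure is 5%. This is not a general error rate: it depends on the size of the common change and on the split, and the documents give neither for the panel.

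The undirected one-sided rule applies to every biomarker test and needs clarifying. Both points deserve correction, but they bear on an exploratory objective. The ORR sample size, the primary analysis and the safety conclusions are unaffected.

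**What to change.** In SAP 7.5.6, add a between-group comparison of change, per disease, as the association analysis. One suitable form is an ANCOVA of the post-baseline value on response group (and separately on progression group), adjusted for baseline. A test of change scores or a model with a group-by-time term would also serve. Report the estimated difference with its confidence interval, and keep the within-group paired results as descriptive.

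In SAP 7.5.1, report two-sided nominal p-values for biomarker tests. If a one-sided test is wanted for a particular marker, state its direction in advance.

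The cost is SAP wording and modest programming on data already planned for collection. There will be fewer nominally significant results, and the between-group test has low power in a single cohort (about 0.26 for a 0.5 SD difference at 12 versus 20). The report should say so, so that a null result is not read as absence of association.
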